2. INTRODUCTION

2.1. Mechanism of Action/Indication

TPX-0046 is a RET/SRC kinase inhibitor with a compact three-dimensional macrocyclic structure designed to efficiently target the RET active kinase conformation and to inhibit clinically-relevant RET fusion proteins and mutations. TPX-0046 has demonstrated potent nonclinical activities against RET and clinically-relevant mutant RETs, especially the SFMs which will potentially confer resistance to current investigational RET inhibitors, and approved TKIs that have RET inhibitory activity which represents a potential unmet medical need. TPX-0046 has minimal activity against the gatekeeper mutation family RET V804X, which includes V804M/L/E. TPX-0046 also inhibits SRC and SRC family members that have the potential to reduce bypass resistance and therefore increase its therapeutic effect. Polypharmacological inhibition of RET and SRC is expected to provide strong anti-tumor efficacy for patients with advanced/metastatic solid cancers harboring oncogenic RET fusions or mutations, especially patients who have developed resistance from current investigational RET inhibitor treatment. The comprehensive nonclinical pharmacology, pharmacokinetic and toxicology evaluation results strongly support a FIH Phase 1/2 clinical trial with TPX-0046 in adult subjects (≥ 18 years) with advanced/metastatic solid tumors harboring oncogenic RET fusions or mutations.

2.2. Background

The RET gene was originally identified as an oncogene in 1985 (Takahashi, 1985) and characterized as a receptor tyrosine kinase (Takahashi, 1987). RET activation regulates multiple signaling pathways (eg, RAS/MAPK/ERK, PI3K/protein kinase [AKT], JAK-STAT) leading to cellular proliferation, migration, and differentiation (Mulligan, 2014). RET plays an essential role in the development and maturation of diverse tissues (Mulligan, 2018). Gain-of-function mutations of RET including amplification, activating point mutations or genomic rearrangements lead to ligand-independent kinase activation have been found in heritable and sporadic tumors. Thyroid carcinoma is the most common endocrine malignancy and accounts for 3%–4% of all cancers in the US with an estimated incidence of 57,000 and deaths of 2000 in 2017 (Siegel, 2017). Germline mutations of *RET* are found in multiple endocrine neoplasia 2A (MEN2A), MEN2B, and familial medullary thyroid carcinoma (MTC) (Mulligan, 2018). Mutations in *RET* have been reported in 43% to 71% of sporadic MTC (Moura, 2009). The somatically occurring rearrangements of the *RET* gene have been identified in 20%–40% of papillary thyroid carcinomas (PTCs) and ~1%–2% NSCLCs (Mulligan, 2018). In addition, RET fusions have been discovered in Spitzoid tumors (~3%), chronic myelomonocytic leukemia, breast, colon, ovarian, salivary gland and inflammatory myofibroblastic tumors (Mulligan, 2018). RET fusions have also been found as a resistance mechanism to EGFR-TKIs in EGFR-mutant NSCLC patients (Bronte, 2019).

2.2.1. RET Targeted Therapies in *RET*+ Disease and Drug Resistance

Multi-kinase inhibitors with activity against RET have been approved for the treatment of a variety of solid and hematological malignancies, such as cabozantinib, vandetanib, lenvatinib, sorafenib for thyroid cancers and ponatinib, alectinib, sunitinib, nintedanib, and regorafenib for

other indications. Multi-kinase inhibitors with moderate activity against RET can achieve confirmed responses in certain patients with *RET*-rearranged or *RET*-mutant cancers but the ORR and DOR are significantly lower than those observed in other oncogene-driven, advanced-stage tumors with matched targeted therapies (Drilon, 2018a). The potent and selective RET inhibitors with minimal off-target activities are likely required for achieving long lasting anti-tumor activity in patients with advanced/metastatic solid tumors harboring an abnormal *RET* gene. Two selective RET inhibitors, pralsetinib (BLU-667) and selpercatinib (LOXO-292) have achieved marked anti-tumor activity in both NSCLC and thyroid cancers (Drilon, 2018b and Subbiah, 2018). Accordingly, selpercatinib was approved by the US Food and Drug Administration (FDA) for adult patients with metastatic *RET* fusion positive NSCLC and adult and pediatric patients 12 years of age and older with *RET* mutant MTC or *RET* fusion positive thyroid cancer refractory to radioactive iodine therapy (RetevmoTM USPI, 2020).

Multiple resistance mutations to vandetanib and cabozantinib, including gatekeeper mutations V804X and SFMs G810X have been reported from preclinical studies (Liu, 2018). The development of RET solvent front mutations have also been reported as resistance mechanisms following treatment with selective RET inhibitors (Solomon, 2020). In RET-rearranged NSCLC, the type of upstream RET fusion partner produced different sensitivity to multi-kinase inhibitors. Lower ORR and shorter median PFS in patients with kinesin family 5B (*KIF5B*)-*RET*+ NSCLC treated with multi-kinase drugs were observed relative to other RET rearrangements (Yoh, 2017; Drilon, 2017). KIF5B-RET leads to a substantial increased *RET* transcription (Kohno, 2012) and strongly activate a RET-SRC-EGFR-FGFR signaling hub (Das, 2017). Inhibition of SRC kinase may interrupt recruitment of multiple receptor tyrosine kinases (RTKs). SRC family tyrosine kinases are known to regulate MTC cellular proliferation in vitro (Liu, 2004). Therefore, a dual inhibitor of both RET and SRC represents a highly-desired therapeutic intervention to maximally target abnormal RET signaling in cancers.

2.3. Nonclinical Overview

2.3.1. Nonclinical Pharmacology

A comprehensive program, including in vitro and in vivo assessments, was conducted on TPX-0046 to evaluate its primary and secondary pharmacodynamic properties, as well as the safety pharmacology to support a FIH Phase 1/2 clinical trial with TPX-0046 in patients with advanced solid tumors harboring genetic alternations in RET. Primary pharmacodynamics of TPX-0046 began with biochemical potency assessments via inhibition of the catalytic activities for multiple recombinant kinases, including the oncogenic RET fusion proteins and mutants as . In cellular assays, the effect of TPX-0046 on RET autophosphorylation, downstream signal effectors, and cell proliferation in human primary cancer cell lines and engineered stable cell lines expressing the targeted fusion RET oncogenes was evaluated as shown in Table 3. Target human plasma exposure to be associated with pharmacological activity , the calculated IC₉₀ value of KIF5B-*RET* solvent front mutation for TPX-0046 is G810R determined in in vitro cell proliferation assays. The in vivo assessment of TPX-0046 on the efficacy of tumor growth inhibition and pharmacodynamic target modulation were performed in a series of mouse xenograft tumor models – both cell line and patient-derived as shown in Figure 1.

[figure not shown]
[figure not shown]

Table 3: Summary of TPX-0046 Activities against RET in Cellular Assays

	Cell Line	TPX-0046
Cell Proliferation IC ₅₀ (nM)		

In the secondary pharmacodynamic studies, TPX-0046 was screened in biochemical assays at 100 nM in two kinase panels: 374 recombinant protein kinases (Reaction Biology) and 157 recombinant kinases (Eurofins). Kinases inhibited by TPX-0046 greater than 90% in either panel were followed up by determining half maximal inhibitory concentration (IC₅₀) values along with selected RTKs which are often inhibited by multi-kinase RET inhibitors. Kinases inhibited in biochemical assays with IC₅₀ < 10 nM were subjected to further testing in cellular assays that measure either cell proliferation or target engagement. TPX-0046 is highly selective with only kinases of the kinases inhibited with less than selectivity over WT RET potency.

[figure not shown]
Kinases inhibited in biochemical assays with IC ₅₀ < 10 nM
were subjected to further testing in cellular assays that measure either cell proliferation or target
engagement . Many kinases with IC ₅₀ values < 10 nM in biochemical assays did no
translate to potency in cellular assays likely due to either the artificial nature of the recombinant
kinase protein or the low concentration of the competitive ligand (ATP in biochemical
assay, > 1 mM in cells).
. SRC family kinases were evaluated in nanoBRET assays
and found to have IC_{50} but the assays may have flaws.
the SRC assay, a luciferase (NanoLuc) is fused to the C-terminal tail of SRC which
has an autoinhibitory phosphorylation site at Tyr530. This construct design might affect the
regulation of SRC kinase conformation". As such,
kinases, and janus kinases are not reported. There were kinases inhibited by TPX-0046 in
cellular assays within 100-fold of TPX-0046 potency toward RET : FGFR1/2
TRKA/B/C, ROS1, and TXK. TPX-0046 inhibits fibroblast growth factor (FGF) receptors with
in biochemical assays as determined in multiple studies (in the
presence of ATP). These results were confirmed in cellular assays with IC50
values of for FGFR1, FGFR2 and FGFR3, respectively. In
biochemical assays,
dependent cell proliferation assays, TPX-0046 has IC50 values of in cells with
TPM3-TRKA, in Ba/F3 cells with TEL-TRKB, and in Ba/F3 cells with TEL-
TRKC. ROS1 had an IC ₅₀ of in a biochemical assay and in a cell proliferation
assay. For TXK, TPX-0046 had a biochemical $IC_{50} =$ and a cellular $IC_{50} =$
Kinases inhibited by TPX-0046 with IC ₅₀ < 10 nM that have only biochemical potency (SRC
family kinases, PEAK1, TIE2) may not all have potent cellular potency. Pseudopodium enriched
atypical kinase 1 (PEAK1) is a pseudokinase with controversial non-receptor tyrosine kinase
activity and has not been reported to be an oncogenic driver as its function is as a molecular
scaffold (O'Rourke, 2018). Taken together, TPX-0046 is highly potent for TPX-0046 with only
one kinase (TRKA) displaying cellular potency within 10-fold of RET cellular potency.
In additional secondary pharmacodynamic studies of 44 purified receptors, ion channels,
transporters, and enzymes, TPX-0046 at only inhibited and
with IC ₅₀ values of , respectively. TPX-0046 had minimal effects on
human ion channels of hNav1.5 (HEK293 cells) and human L-type C _{av} 1.2
(IC ₅₀ , HEK293 cells), and moderate effect on human ether-à-go-go-related gene
(hERG) (CHO cells).
Taken together TPV 0046 has demonstrated notent nonclinical activities against PET and

[figure not shown]
Taken together, TPX-0046 has demonstrated potent nonclinical activities against RET and clinically-relevant mutant RETs, especially the SFMs which will likely confer resistance to any therapy that has RET inhibitory activity, including investigational selective RET inhibitors, which represents a potential unmet medical need. TPX-0046 is an inhibitor of SRC tyrosine kinase in in vitro assays. Aberrant activation of SRC signaling contributes to diverse aspects of tumor development and treatment resistance. The inhibition of the SRC kinase has the potential to reduce the recruitment of multiple RTKs involved in bypass resistance and therefore increase the therapeutic effect of TPX-0046. Therefore, pharmacological inhibition by TPX-0046 of a broad range of oncogenic *RET* mutations and fusion proteins is expected to provide anti-tumor efficacy for *RET*+ cancer patients, especially patients who have developed resistance. These

[figure not shown]
comprehensive in vitro and in vivo evaluation results strongly support a FIH Phase 1/2 clinical trial with TPX-0046 in adult patients with advanced solid tumors harboring an oncogenic *RET* fusion or mutation.

2.3.2. Nonclinical Pharmacokinetics

The absorption, distribution, metabolism, excretion (ADME) properties as well as drug-drug interaction profile of TPX-0046 were characterized in various animal and human in vitro and in vivo systems.

Overall, the nonclinical ADME, and drug-drug interaction assessments of TPX-0046 support the advancement for clinical evaluation.

2.3.3. Nonclinical Toxicology

A comprehensive IND-enabling nonclinical safety assessment program has been conducted consistent with the International Council for Harmonisation of Technical Requirements for Pharmaceuticals for Human Use (ICH) guideline, "Nonclinical Evaluation for Anticancer Pharmaceuticals (S9)," and is comprised of single- and repeat-dose exploratory toxicology

studies and definitive 28-day toxicology studies conducted in two mammalian species (rat and monkey), selected based on comparable metabolite profiles in humans, using the clinically-relevant route (oral) and schedule (once daily) of administration (ICH Guidance: S9, 2009). The pivotal 28-day repeat dose toxicity studies in rats and cynomolgus monkeys demonstrated evidence of inflammatory stimulation, effects on growing bone physes, and soft tissue mineralization, with adequate exposure margins for the adult patient population.

2.4. Basis of Clinical Starting Dose of TPX-0046-01 FIH Study

For the recommended starting dose of TPX-0046-01 FIH study, an integrated approach in accordance with regulatory guidance, scientifically justified using all available nonclinical data including PK, pharmacodynamics, and toxicity was applied. Based on the projected human PK at the proposed starting dose of 10 mg QD, the exposure-based margins relative to the toxicokinetic parameters at STD10 or highest non-severe toxic dose (HNSTD) are summarized.

3. STUDY OBJECTIVES AND ENDPOINTS

Based on the totality of clinical information available, the Sponsor has decided to discontinue further development of TPX-0046 due to the inability to achieve and optimize a dose that could provide a positive benefit-risk profile in the current treatment landscape for *RET* mutant TKI naïve and pretreated setting. This decision was communicated to study sites on 03 October 2022. As such, no new subjects will be enrolled in this study, which will close after all active subjects have completed treatment. Subjects currently receiving treatment in this study will continue treatment at the discretion of the Investigators until need for discontinuation (Section 8.7) or ability to move to alternative care is identified. As such, a synoptic CSR will be generated and submitted to health authorities.

Primary Objectives	Primary Endpoints		
Phase 1:	Phase 1:		
 Evaluate the safety and tolerability of TPX-0046 at selected doses Determine the maximum tolerated dose (MTD) and/or Recommended Phase 2 Dose (RP2D) of TPX-0046 	 Incidence of first cycle dose-limiting toxicities (DLTs) of TPX-0046 administered orally in a 28-day cycle MTD and RP2D 		

4. STUDY DESIGN

4.1. Overall Study Design

This is a Phase 1/2 multi-center, first-in-human (FIH), open-label study designed to evaluate the safety, tolerability, PK, and efficacy of the novel RET/SRC inhibitor TPX-0046 in adult subjects with advanced/metastatic solid tumors harboring oncogenic *RET* fusions or mutations. The global study consists of two portions as shown in Figure 2: 1) Phase 1 Dose Escalation, Food Effect Sub-study, and Dose Expansion in 6 cohorts, and 2) Phase 2 preliminary efficacy evaluation in six defined subject cohorts.

As the study enrollment will close prior to completing Phase 1 dose escalation, the Phase 1 food effect substudy, Phase 1 dose expansion, and Phase 2 activities will not take place.

Figure 2: Study Design

4.1.1.1. Dose Escalation Schema

The dose escalation schema is illustrated in Table 5. No further dose escalation will occur; dose level 9 was the last to enroll subjects prior to closing study enrollment. DLTs will be evaluated independently in any given dosing regimen.

4.1.1.2. Dose-Limiting Toxicity

[figure not shown]
Subjects are eligible for DLT evaluation if they experience a DLT after at least one dose of the TPX-0046, or do not experience a DLT after taking at least 75% of the doses expected during the DLT evaluation period. Subjects who do not fulfill these requirements and who discontinue study participation before completing the DLT evaluation period will not be replaced. The DLT evaluation period is defined as 28 days following the first dose of the dose regimen administered in Cycle 1

The following AEs, excluding toxicities clearly related to disease progression or intercurrent illness, will be considered DLTs (Table 6).

Table 6: Criteria for Defining Dose-Limiting Toxicities

Category	Criteria				
Toxicities resulting in an excessive number of missed doses	Inability to deliver at least 75% of the planned dose intensity of TPX-0046 treatment during the DLT evaluation period (ie, at least 21 days of dosing in a 28-day cycle, beginning in Cycle 1) because of toxicity excluding toxicities clearly related to disease progression or intercurrent illness				
Hematologic toxicities	 CTCAE grade ≥ 4 neutropenia (absolute neutrophil count [ANC] < 0.5 × 10⁹/L) CTCAE grade ≥ 4 platelet count decrease (platelets < 25 × 10⁹/L) or CTCAE grade ≥ 3 (< 50× 10⁹/L- 25 × 10⁹/L) associated with clinically significant bleeding or requiring platelet transfusion CTCAE grade ≥ 4 anemia CTCAE grade ≥ 3 febrile neutropenia (defined as ANC < 1,000/mm³ with a single temperature of ≥ 38.3 °C [≥ 101 °F] or a sustained temperature of ≥ 38 °C [≥ 100.4 °F] for > 1 hour) 				
Renal	• CTCAE grade ≥ 3 creatinine increase (> 3.0 x baseline or > 3-6 × upper limit of normal [ULN])				
Hepatic	 CTCAE grade ≥ 3 total bilirubin elevation (> 3 × ULN) CTCAE grade ≥ 2 total bilirubin elevation (> 1.5 × ULN) AND CTCAE grade ≥ 2 alanine aminotransferase (ALT) or aspartate aminotransferase (AST) elevation (> 3 × ULN) CTCAE grade 3 ALT elevation (> 5 × ULN) that does not resolve to at least grade ≤ 1 within 7 days or any grade > 4 ALT elevation CTCAE grade 3 AST elevation (> 5 × ULN) that does not resolve to at least grade ≤ 1 within 7 days or any grade > 4 AST elevation 				
Pancreatic	CTCAE grade 3 serum increased with clinical symptoms or any grade ≥ serum				
Cardiac	• CTCAE grade ≥ 3				

4.1.1.3. Maximum Tolerated Dose

The MTD is defined as the highest dose level of TPX-0046 observed to cause a DLT in fewer than 33% of the treated subjects in the first treatment cycle (ie, Cycle 1, 28 days). If there are 2 subjects who experience DLTs among the first 3 subjects enrolled, or there is a second DLT in up to 6 subjects enrolled at any dose level, the MTD will have been exceeded, and no additional subjects will be enrolled at that dose level. The MTD will then be established at the prior dose level. If the prior dose cohort has only 3 enrolled subjects, the cohort will be expanded in up to 6 total subjects.

4.1.1.4. Safety Review Committee

For Phase 1 dose escalation of the study, a Safety Review Committee comprised of at minimum the Sponsor Medical Monitor and study Investigators will review all relevant safety and other relevant clinical data (including DLTs).

4.2. Recommended Dose Modifications

Every effort should be made to administer TPX-0046 on the planned dose and schedule.

In the event of significant toxicity, dosing may be delayed and/or reduced as described below. In the event of multiple toxicities, dose modification should be based on the worst toxicity observed. Subjects are to be instructed to notify the Investigators at the first occurrence of any adverse symptom.

Dose modifications may occur in one of three ways:

- Within a cycle: dosing interruption until adequate recovery, and dose reduction, if required, during a given treatment cycle;
- Between cycles: next cycle administration may be delayed due to persisting toxicity when a new cycle is due to start;
- In the next cycle: dose reduction may be required in a subsequent cycle based on toxicity experienced in the previous cycle.

4.2.1. Dose Interruptions

Dose interruptions may occur in the event of a treatment-related toxicity or a non-treatment-related issue (eg, elective surgery).

Appropriate follow-up assessments should be done until adequate recovery occurs as assessed by the Investigator. Criteria required before treatment can resume are described in the dose modification table (see Table 7).

Doses may be held as needed until toxicity resolution. Depending on when the AE is resolved, a treatment interruption may lead to the subject missing all subsequent planned doses within that same cycle or even to delay the initiation of the subsequent cycle. Subjects not recovering from TPX-0046-related toxicity to grade ≤ 1 since the last dose must discontinue TPX-0046 treatment.

If the AE that led to the treatment interruption recovers within the same cycle, then re-dosing in that cycle is allowed. Doses omitted for toxicity are not replaced within the same cycle. The need for a dose reduction at the time of treatment resumption should be based on the criteria defined in Table 7 unless otherwise agreed to following discussion between the Investigator and the Medical Monitor.

In the event of a treatment interruption for reasons other than treatment-related toxicity (eg, elective surgery) lasting treatment resumption must be discussed with the Medical Monitor.

Every effort should be made to maintain the tumor assessments and visit scheduling as described in the Schedules of Activities.: Regardless of dose interruptions, cycle lengths will remain 28 days and evaluations are to be performed according to the schedules.

4.2.2. Dose Delays

Re-treatment following treatment interruption for treatment-related toxicity may not occur until the event has resolved to grade ≤ 1 or baseline of the event.

If a treatment delay results from worsening of hematologic or biochemical parameters, the frequency of relevant laboratory assessments may be increased as clinically indicated.

Refer to the Dose Reductions section for AEs requiring dose reduction at the time of treatment resumption (Section 4.2.3).

If subjects require discontinuation of TPX-0046 for study, then study treatment should be permanently discontinued, unless the Investigator's benefit/risk assessment suggests otherwise after discussion with the Medical Monitor.

Regardless of dose interruptions, cycle lengths will remain 28 days and evaluations are to be performed according to the schedules.

4.2.3. Dose Reductions

Following dosing interruption or cycle delay due to toxicity, the TPX-0046 dose may need to be reduced when treatment is resumed. No further dose reduction for the remaining subjects will be allowed.

Dose reduction of TPX-0046 by one and, if needed, 2 dose levels (Table 7) will be allowed depending on the type and severity of toxicity encountered. As a guide, subjects currently being treated at 30 mg QD should reduce one dose level to 20 mg QD. If a subject is being treated at 40 mg QD and requires dose reduction, they should dose reduce to 30 mg QD initially and then 20 mg QD if needed.

For subjects who undergo a dose reduction for an AE other than a protocol-defined DLT, a subsequent re-escalation of the dose may be considered appropriate if deemed safe by the Investigator and after consultation with the Sponsor's Medical Monitor. Subjects requiring more than 2 dose reductions will be discontinued from the treatment and entered in the follow-up phase, unless otherwise agreed between the Investigator and Medical Monitor. All dose modifications/adjustments must be clearly documented in the subject's source notes and case report form (CRF).

All dose reduction cases should be discussed with the Medical Monitor unless specifically outlined in the protocol. In cases where no specific dose adjustment requirements for CTCAE version 5.0 grade 2 treatment-related toxicity exist, Investigators should always manage their subjects according to their medical judgment, which may include dose reduction or interruption based on the particular clinical circumstances in consultation with the Medical Monitor.

for subjects with DLTs is not allowed in the Phase 1 study. Subjects experiencing a DLT (if applicable) once adequate recovery is achieved.

Recommended dose reductions are described in Table 7.

Table 7: Dose Modifications for Adverse Events (CTCAE version 5.0)

Toxicity	CTCAE Grade 1*	CTCAE Grade 2*	CTCAE Grade 3	CTCAE Grade 4
Hematologic	Continue at same dose level.	Continue at same dose level.	Withhold dose until toxicity is grade ≤ 2, or has returned to baseline, then resume treatment at the same dose level or reduce by one dose level as per the Investigator's discretion. Grade 3 lymphopenia without other dose- limiting events (eg, opportunistic infection) may continue study treatment without interruption.	Discontinue treatment permanently.
Non-Hematologic	Continue at same dose level.	Continue at same dose level.	Withhold dose until toxicity is grade ≤ 1 or has returned to baseline, then reduce by one dose level and resume treatment.	Discontinue treatment permanently.
Pneumonitis (occurred in the absence of disease progression, pulmonary embolism, positive cultures or radiation effect)	Asymptomatic, radiographic findings only: No need for dose adjustment. Initiate appropriate monitoring. Symptomatic: Withhold current dose until toxicity has returned to baseline. Rule out infection and consider initiating treatment with corticosteroids. Then resume treatment at the same dose. Discontinue permanently if pneumonitis recurs or if failure to recover after 6 weeks of study treatment hold and steroid treatment.	Withhold current dose until toxicity has returned to baseline. Rule out infection and consider initiating treatment with corticosteroids. Then resume treatment at one dose level lower. Discontinue permanently if pneumonitis recurs or if failure to recover after 6 weeks of study treatment hold and steroid treatment.	Discontinue treatment permanently.	Discontinue treatment permanently.

Toxicity	CTCAE Grade 1*	CTCAE Grade 2*	CTCAE Grade 3	CTCAE Grade 4
AST or ALT elevation	Continue at same dose level.	Continue at same dose level. Withhold current dose if concurrent CTCAE grade ≥ 2 total bilirubin elevation (> 1.5 x ULN).	Withhold current dose until resolves to grade ≤ 1.	Discontinue treatment permanently.
Prolonged QTc	Assess electrolytes and concomitant medications. Correct any electrolyte abnormalities, or hypoxia. Continue at the same dose level.	Assess electrolytes and concomitant medications. Correct any electrolyte abnormalities, or hypoxia. Continue at the same dose level.	Withhold dose. Assess electrolytes and concomitant medications. Correct any electrolyte abnormalities, or hypoxia. Upon recovery to grade ≤ 1: if no other cause for QTc prolongation is found or is considered drug-related resume treatment at 1 dose level lower.	Discontinue treatment permanently.
Dizziness ataxia, or weakness	Continue at same dose level	Withhold current dose until toxicity is grade ≤1 or has returned to baseline	Withhold dose until toxicity is grade ≤1 or has returned to baseline	Withhold dose until toxicity is grade ≤1 or has returned to baseline, then reduce by 1 dose level and resume treatment; or discontinue treatment as per the Investigator's discretion after discussion with Medical Monitor

Abbreviations: ALT = Alanine aminotransferase; AST = Aspartate aminotransferase; CNS = central nervous system; CTCAE = Common Terminology Criteria for Adverse Events, version 5.0; ULN = upper limit of normal

^{*}Cycle will not be extended to cover for the missing doses. In cases where no specific dose adjustments for CTCAE grade 1 or grade 2 treatment-related toxicity are provided, Investigators should always manage their subjects according to their medical judgment, which may include dose reduction or interruption based on the particular clinical circumstances.

4.2.4. Dose Modifications:

In all subjects, mitigating should be discussed with the Medical Monitor. Additional dosing guidelines for are provided in Table 8.

Table 8: Recommended Dose Modification Guidelines

TPX-0046 Dose Modification ^a

^aDose reduction or interruption should be implemented upon consultation with the Medical Monitor.

4.2.5. **Dose Modifications:**

exams including will be conducted per the Schedules of Activities

For adverse reactions follow the dose modification guidelines provided in Table 9.

Table 9: Dose Modification Guidelines

CTCAE Grade	Parameters	TPX-0046 Dose Modification
1	Asymptomatic; clinical or diagnostic observations only	Withhold current dose until toxicity has returned to baseline. If resolves within 4 weeks, resume Then, consider re-escalation if no recurrence for 4 weeks. If stable for 2 consecutive exams but not resolved, resume
2	Symptomatic; moderate decrease in and or less decreased from known baseline)	Withhold current dose until toxicity has returned to baseline. If resolves within 4 weeks, may resume
3	Symptomatic with marked decrease in or more than of decreased from known baseline,	Withhold current dose until toxicity has returned to baseline. If resolves within 4 weeks, may resume
4	Best corrected or worse in the	Discontinue treatment permanently

^{*}National Cancer Institute Common Terminology Criteria for Adverse Events (NCI-CTCAE) v5.0.

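### Section 4.2.3 bars further dose reduction for the remaining subjects, then allows it and sets out steps for it; Section 4.2.2 and Table 7 also give different restart grades after grade 3 hematologic toxicity

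*Combined protocol and SAP*

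**What the plan says.** **Dose reduction.** Section 4.2.3 opens by saying that the dose may have to be lowered when treatment resumes after an interruption or delay for toxicity. The next sentence reads: "No further dose reduction for the remaining subjects will be allowed". The following paragraph says that reduction "by one and, if needed, 2 dose levels (Table 7) will be allowed", depending on the type and severity of toxicity. It continues: "As a guide, subjects currently being treated at 30 mg QD should reduce one dose level to 20 mg QD", and it gives two successive steps for subjects on 40 mg QD. Table 7, in the same section, builds reduction into several of its actions. For a grade 3 non-hematologic event, for example, it says: "Withhold dose until toxicity is grade ≤ 1 or has returned to baseline, then reduce by one dose level and resume treatment".

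**Restart after interruption.** Section 4.2.1 names Table 7 as the place where the criteria for resuming are found. It also says that subjects whose drug-related toxicity does not recover to grade 1 or lower must stop treatment. Section 4.2.2 does not allow re-treatment after treatment-related toxicity until the event is at grade 1 or lower, or at baseline, and it makes no exception for hematologic events. The grade 3 hematologic cell of Table 7 sets the threshold at grade 2 or lower, or baseline.

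**Discretion.** Section 4.2.1 bases the need for reduction on Table 7 "unless otherwise agreed to following discussion between the Investigator and the Medical Monitor". Section 4.2.3 calls the Table 7 reductions recommended and adds: "All dose reduction cases should be discussed with the Medical Monitor unless specifically outlined in the protocol".

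**The concern.** An investigator treating one of the remaining subjects finds opposing instructions for the same event. After a grade 3 non-hematologic event resolves, Table 7 calls for restart one level lower, while the opening paragraph of Section 4.2.3 does not allow that reduction. Sites could therefore handle the same toxicity differently, and each could cite the protocol.

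Medical Monitor review may not catch this. Reductions that the protocol specifically outlines are exempt from discussion, and a reduction made under a Table 7 cell fits that description.

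The conflict also bears on who stays on drug. Section 8.7 lists an adverse event that cannot be managed with dose modifications as a possible reason for stopping, so it matters whether reduction is available. No effect on the primary endpoint (first-cycle DLTs) is claimed. What is at stake is the safe and consistent handling of subjects still being dosed.

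**Working it through.** The plan gives no figure to reproduce here. The check sets the passages side by side and counts the cells affected.

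**1. Do the bar and the permission cover the same subjects?**
- Section 10.2.1: 41 subjects have enrolled across 9 dose levels, and enrollment is closed. Everyone still dosed is therefore a remaining subject.
- Section 7.1 uses the same term for the subjects who are to be told that enrollment has closed.
- The permission cannot be read as covering past subjects only, because its guide addresses subjects now on 30 mg QD.
- Section 4.2.1 also relies on Table 7 for reductions, and Section 4.2.2 sends the reader to Section 4.2.3 for events that require one.

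No other on-treatment group exists to which the permission could apply, so the two statements collide.

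**2. How much of Table 7 is affected?** The table has 6 toxicity rows × 4 grades = 24 cells.

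| Cell | Role of reduction | Can the site also comply with the bar? |
|---|---|---|
| Non-hematologic, grade 3 | Part of the stated action | No |
| Pneumonitis, grade 2 ("Then resume treatment at one dose level lower") | Part of the stated action | No |
| Prolonged QTc, grade 3 ("if no other cause for QTc prolongation is found or is considered drug-related resume treatment at 1 dose level lower") | Part of the action when its condition is met | No, when the condition is met |
| Hematologic, grade 3 | Option; same dose level also allowed | Yes, by not using the option |
| Dizziness, ataxia or weakness, grade 4 | Option; stopping also allowed | Yes, by not using the option |

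Cells calling for reduction: 3. Cells offering it: 2. Total 3 + 2 = 5. The remaining 24 − 5 = 19 cells name no reduction, although the table's footnote leaves grade 1 or 2 reductions to judgment where no adjustment is given.

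**3. Restart grade.** Take a treatment-related grade 3 hematologic event, baseline grade 0 or 1, now recovered to grade 2.
- Table 7: restart permitted.
- Section 4.2.2: restart not permitted.
- Section 4.2.1: Table 7 supplies the restart criteria, yet treatment must stop if grade 1 or lower is not reached.

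If baseline was already grade 2, Section 4.2.2 and Table 7 agree through their baseline clauses. Table 7 also lets grade 3 lymphopenia without other dose-limiting events continue uninterrupted, so no restart question arises there.

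**4. Secondary: coverage of the guide, if reductions remain allowed.** Doses in Table 5 after any lead-in, levels 1 to 9, are 10 QD, 20 QD, 10 BID, 30 QD, 30 QD, 20 BID, 40 QD, 20 BID and 10 BID (mg). The guide gives steps from 30 mg QD and 40 mg QD, that is, levels 4, 5 and 7, or 3 of 9. It gives none for the other 9 − 3 = 6 (levels 1, 2, 3, 6, 8 and 9). The level numbers do not fill the gap, because they do not follow daily dose: levels 2 and 3 share 20 mg/day, and level 9 is labelled a decrease.

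**The case against.** - **The word *further*.** It might mean beyond the one or two levels set out in the next paragraph, in line with the rule that subjects needing more than 2 reductions come off treatment. The text does not say this, and the reading sits badly with the same section, which lets the Investigator and Medical Monitor agree otherwise beyond 2 reductions. Reading it as beyond reductions already made would still bar a new reduction under Table 7.
- **The count.** Only 3 cells force a conflict, because the other 2 can be followed without reducing. That is correct, and the two groups are kept apart here.
- **Discretion.** Table 7 is a recommendation, and Section 4.2.1 allows other arrangements after discussion. This softens the conflict but does not say which statement governs. How often sites would reduce without noticing the bar is not known.
- **Table 7 as the specific rule.** Section 4.2.1 points to Table 7 for resumption, so its hematologic row could override the general rule in Section 4.2.2. But Section 4.2.2 states no exception, and Section 4.2.1 itself requires stopping without recovery to grade 1 or lower. That last sentence may have lost a time limit to redaction, so its force is uncertain. The conflict between Section 4.2.2 and Table 7 does not depend on it.
- **The guide.** It is offered as a guide, and the regimens still in use are not stated. If only subjects on 30 or 40 mg QD remain, there is no gap. This item is missing detail, and the conclusion does not rest on it.
- **Limited exposure.** Enrollment is closed and drug supply ends in July 2023. This narrows the exposure without removing the contradiction.

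**Conclusion.** The concern holds. Section 4.2.3 contradicts itself on whether remaining subjects may have their dose reduced: 3 of 24 Table 7 cells cannot be followed together with the bar (the QTc cell when its condition is met), and 2 more offer an option that the bar removes. The hematologic restart grade also conflicts between Section 4.2.2 and Table 7, but only for treatment-related grade 3 events with a baseline below grade 2.

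The conclusion rests on the current text. Nearby sentences are redacted, but the bar, the permission, and the Section 4.2.2 and Table 7 criteria are complete as they stand. The number of subjects affected cannot be derived, because the documents do not say how many of the 41 are still on drug or on which regimens. The point must be fixed because it concerns safety instructions in current use. No view is taken on which rule is right.

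**What to change.** - Reconcile Section 4.2.3 so that one statement on dose reduction for the remaining subjects stands, and bring the five Table 7 cells that call for or offer a reduction into line with it.
- Reconcile the restart criterion after grade 3 hematologic toxicity across Sections 4.2.1 and 4.2.2 and Table 7.
- If reductions remain allowed, state what one dose level means for each regimen still in use that the guide does not cover.

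Which rule and which steps apply is for the sponsor's clinical team. The cost is the wording of an amendment or clarification letter, with no new data and no additional subjects.
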